Appendix 3 Dosing instructions

Dose 2 mg/kg/day (max 100 mg/day)

Body weight (kg)	IMP dose administered (mg)	Range of dose received (mg/kg)
10-12	20	1.7-2.0
13-17	30	1.8-2.3
18-22	40	1.8-2.2
23-27	50	1.9-2.2
28-32	60	1.9-2.1
33-37	70	1.9-2.1
38-42	80	1.9-2.1
43-47	90	1.9-2.1
≥48	100	≤2.1

Dose 4 mg/kg/day (max 200 mg/day)

Body weight (kg)	IMP dose administered (mg)	Range of dose received (mg/kg)
10-11	40	3.6-4.0
12-13	50	3.8-4.2
14-16	60	3.8-4.3
17-18	70	3.9-4.1
19-21	80	3.8-4.2
22-23	90	3.9-4.1
24-28	100	3.6-4.2
29-31	120	3.9-4.1
32-33	130	3.9-4.1
34-36	140	3.9-4.1
37-38	150	3.9-4.1
39-41	160	3.9-4.1
42-43	170	4.0
44-46	180	3.9-4.1
47-48	190	4.0
≥49	200	≤4.1

Appendix 4 Guidance for glucocorticoid tapering

Tapering of the glucocorticoid dose is suggested at an interval of every second week. The table below describes **an example** of tapering steps if the start dose is = 1 mg/kg.

The tapering can be commenced earliest at the Week 2 visit and if the patient has reached at least ACR50 response with no fever in the preceding 7 days.

	Body weight						Weight-based dose
	10-20 kg	20-30 kg	30-40 kg	40-50 kg	50-60 kg	≥60 kg	
Stable dose at baseline	10 mg	20 mg	30 mg	40 mg	50 mg	60 mg	1 mg/kg (max 60mg)
Dose prescribed at first tapering step (earliest at Week 2)	7.5 mg	15 mg	22.5 mg	30 mg	37.5 mg	45 mg	0.75 mg/kg
Dose prescribed at second tapering step (2 weeks after tapering commences)	5 mg	10 mg	15 mg	20 mg	25 mg	30 mg	0.5 mg/kg
Dose prescribed at third tapering step (4 weeks after tapering commences)	2.5 mg	5 mg	7.5 mg	10 mg	12.5 mg	15 mg	0.25 mg/kg
Dose prescribed at fourth tapering step (6 weeks after tapering commences)	1 mg	2.5 mg	2.5 mg	5 mg	5 mg	7,5 mg	0,12 mg/kg
Dose prescribed at fifth tapering step (8 weeks after tapering commences)	off	off	off	off	off	off	off

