6.4.6 Prior and concomitant therapy

Intraarticular, intramuscular and intravenous administration of glucocorticoids are prohibited within 4 weeks prior to randomization and during the study. Other administration of glucocorticoid treatment is allowed as concomitant medication during the study if the patient has had a stable dose for at least 1 week prior to randomization. Maximum dose allowed is 1 mg/kg/day (max 60 mg/day). If the patient is on glucocorticoid treatment, the dose can be tapered starting earliest at the Week 2 visit. The patient must have reached at least ACR50 response with no fever in the preceding 7 days at the visit initiating tapering. A suggested glucocorticoid tapering schedule is provided in Appendix 4. All other glucocorticoid treatment is prohibited during the study except topical and inhaled.

Methotrexate is allowed as concomitant medication during the study if the patient has had a stable dose for at least 8 weeks prior to randomization. The dose should remain stable throughout the study as long as it is well tolerated. If prior treatment with methotrexate, discontinuation is required to be at least 4 weeks prior to randomization.

Initiation of continuous NSAID treatment is prohibited during the study. However on demand treatment is allowed.

Narcotic analgesics are not allowed 24 hours prior any study visit.

Use of the following treatments are not allowed concomitantly with the IMP (wash-out periods before randomization are stated in the exclusion criteria see 6.3.2):

- Intraarticular, intramuscular or intravenous administration of glucocorticoids
- Intravenous immunoglobulins

- Canakinumab or any other IL-1 inhibitor
- Tocilizumab, rituximab or any other immunomodulatory medication
- Etanercept, adalimumab, infliximab, or any other TNF inhibitor (investigational or marketed)
- Dapsone or mycophenolate mofetil, Leflunomide, thalidomide or cyclosporine, 6-Mercaptopurine, azathioprine, cyclophosphamide, chlorambucil, or any other immunosuppressant
- Use of any other investigational drug

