6.5.1.5 Week 2 visit

The visit should be scheduled as close as possible to 24 hours after last IMP dose.

Assessments conducted at the visit are the ACR variables, physical examination including a complete joint count, vital signs, concomitant medication, and global assessment of the patient disease related pain. If any fever or rash attributable to the disease has occurred during the 7 days preceding the Week 2 visit, this will be recorded. Data from the patient diary will support the evaluation.

Blood samples will be collected for central laboratory assessments, immunogenicity assessments, IL-1Ra/anakinra serum concentration assessments and exploratory inflammatory biomarkers. Adverse events as well as number of days of absenteeism from school or work since previous visit (also recorded for guardians where appropriate) will be recorded. The patient diary will be reviewed to confirm that instructions are followed and IMP covering the period until next visit will be dispensed. After all assessments have been performed, the daily IMP administration can occur.

If the patient is on glucocorticoid treatment the possibility to start tapering can be commenced earliest at the Week 2 visit. The patient should have reached at least ACR50 response with no fever in the preceding 7 days at the visit initiating tapering. See Appendix 4 for suggested glucocorticoid tapering instructions.

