### 12.4.5 Glucocorticoid tapering

The number and percentage of patients who have initiated tapering of glucocorticoids at Week 12 will be presented.

For patients that initiated tapering the percentage decrease of glucocorticoid dose at Week 2, Week 4, Week 6, Week 8 and Week 12 compared to baseline will be presented with descriptive statistics. The number of patients that have been able to decrease the glucocorticoid dose with at least 50 % from baseline to Week 12 will be presented.

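### Appendix 4's example steroid taper is stated for a 1 mg/kg start, but its mg doses are set at the lower edge of wide weight bands that share edges, so they disagree with its own mg/kg column at most weights below 60 kg

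*Protocol*

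**What the plan says.** Protocol Appendix 4 is guidance. It says "Tapering of the glucocorticoid dose is suggested at an interval of every second week" and presents its table as an example "of tapering steps if the start dose is = 1 mg/kg". The columns are body-weight bands (10-20, 20-30, 30-40, 40-50, 50-60 and ≥60 kg), followed by a weight-based column. The rows are the stable baseline dose and five steps, the first labelled "Dose prescribed at first tapering step (earliest at Week 2").

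- Baseline: 10, 20, 30, 40, 50, 60 mg; 1 mg/kg, capped at 60 mg.
- Step 1: 7.5, 15, 22.5, 30, 37.5, 45 mg; 0.75 mg/kg.
- Step 2: 5, 10, 15, 20, 25, 30 mg; 0.5 mg/kg.
- Step 3: 2.5, 5, 7.5, 10, 12.5, 15 mg; 0.25 mg/kg.
- Step 4: 1, 2.5, 2.5, 5, 5, 7.5 mg; 0.12 mg/kg. Step 5: off.

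Protocol 6.4.6 sets a ceiling ("Maximum dose allowed is 1 mg/kg/day (max 60 mg/day") and points to the table: "A suggested glucocorticoid tapering schedule is provided in Appendix 4". Section 6.5.1.5 (Week 2) does the same: "See Appendix 4 for suggested glucocorticoid tapering instructions". Section 6.5.1.6 repeats that pointer for Weeks 4 and 8. On the analysis side, SAP 12.4.5 summarises, for patients who began tapering, the "percentage decrease of glucocorticoid dose at Week 2, Week 4, Week 6, Week 8 and Week 12 compared to baseline", and counts those with at least a 50% reduction by Week 12.

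**The concern.** The table states one case, a start at 1 mg/kg, and then gives that patient two doses for the same step: one in the weight-band cell and one in the mg/kg column. For most weights below 60 kg the two differ, and the band cell is always the lower. The bands also share the edges 20, 30, 40, 50 and 60 kg, so a patient exactly at an edge falls in two columns.

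This is the protocol's only numeric taper, and three sections send investigators to it. The practical risk is an unintended faster steroid reduction, largest in the smallest children. The statistical risk is that the descriptive percentage decreases partly reflect which part of the table a site used.

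**Working it through.** **Inputs.** The cells and bands are those of Appendix 4. Mid-band weights are 15, 25, 35, 45 and 55 kg.

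**1. Reproducing the cells.** Cell = mg/kg value × lower edge. For step 1: 0.75 × 10, 20, 30, 40, 50 = 7.5, 15, 22.5, 30, 37.5 mg, exactly as printed. The same rule reproduces baseline, step 2 and step 3. At whole-kg weights from 10 to 59, cell and column agree in these rows at only 5 of 50 weights: 10, 20, 30, 40 and 50 kg.

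**2. What the printed baseline means in mg/kg.** At each lower edge it is 1.00 mg/kg. At the upper edges it is 10/20 = 0.50, 20/30 = 0.67, 30/40 = 0.75, 40/50 = 0.80 and 50/60 = 0.83 mg/kg. So the mismatch already sits in the baseline row.

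**3. First cut within one column.** 1 − 7.5/10 = 1 − 15/20 = 1 − 22.5/30 = 1 − 30/40 = 1 − 37.5/50 = 25%. The mg/kg column gives 1 − 0.75/1 = 25%. Each column is consistent with itself.

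**4. Cut for a patient truly on 1 mg/kg who is moved to the band cell.** Cut = 1 − cell/weight.

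| Weight | Step 1 | Step 2 | Step 3 |
|---|---|---|---|
| 15 kg | 1 − 7.5/15 = 50.0% | 66.7% | 83.3% |
| 25 kg | 1 − 15/25 = 40.0% | 60.0% | 80.0% |
| 35 kg | 1 − 22.5/35 = 35.7% | 57.1% | 78.6% |
| 45 kg | 1 − 30/45 = 33.3% | 55.6% | 77.8% |
| 55 kg | 1 − 37.5/55 = 31.8% | 54.5% | 77.3% |
| mg/kg column | 25% | 50% | 75% |

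In mg, a 15 kg child on 15 mg is pointed to 7.5 mg by the cell and 0.75 × 15 = 11.25 mg by the column. A 19 kg child on 19 mg is pointed to 7.5 mg (60.5% cut) and 0.75 × 19 = 14.25 mg (25% cut).

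**5. Shared edges.** The two columns give first doses of 7.5 or 15 mg at 20 kg, 15 or 22.5 mg at 30 kg, 22.5 or 30 mg at 40 kg, 30 or 37.5 mg at 50 kg, and 37.5 or 45 mg at 60 kg.

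**6. Effect on the summaries.** From the table in item 4, the two readings differ at mid-band by 7 to 25 percentage points at step 1 (31.8 − 25 to 50 − 25), 5 to 17 at step 2 and 2 to 8 at step 3. For a taper begun at Week 2 or Week 4 and kept on schedule, the patient is off steroid by Week 12 on either reading. For a Week 8 start, Week 12 is step 3: 75% by the column and 77 to 83% by the mid-band cells. If the dose counted is the one in force before that day's step, it is step 2: 50% against 55 to 67%. The at-least-50% criterion is met in every case.

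**7. Comparison with Appendix 3.** The study-drug table uses bands that do not overlap and prints the "Range of dose received (mg/kg"). Its bounded bands stay within about 17% of target (worst case 20 mg at 12 kg: 1.67 against 2 mg/kg, −16.7%). Appendix 4's baseline cells fall up to 50% below 1 mg/kg.

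**The case against.** The best defence is that the table is optional and internally proportional. It is headed as guidance, called an example and described as suggested wherever it is cited. Each mg column shows its own starting dose, so a prescriber can see that the 10 mg column is for someone on 10 mg. Setting cells at the lower edge may also be deliberate: a 15 mg baseline for 10-20 kg would breach the 1 mg/kg ceiling for a 10 kg child. That reason is an inference; the protocol does not give it.

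Much of this stands. A reader might infer that the mg cells themselves prescribe a first cut of 32 to 50%. They do not: that range arises only when a true 1 mg/kg start is combined with a band cell. What does not stand is that the defence reconciles the table. The columns are labelled by weight, not starting dose, and the stated case is 1 mg/kg. Starting from the printed baseline fails as well: a 15 kg child on the printed 10 mg would be given 11.25 mg at step 1 by the mg/kg column, above baseline.

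Two further inferences are not supported. One is that patients above 60 kg get little or no first cut from the mg/kg column. The table gives them their own column (60 mg, then 45 mg, a 25% cut) and caps the baseline at 60 mg, so that reading requires ignoring a printed cell. The other is that the step 4 cells are also wrong: 0.12 mg/kg at the lower edges is 1.2, 2.4, 3.6, 4.8, 6.0 and 7.2 mg against the printed 1, 2.5, 2.5, 5, 5 and 7.5 mg, which looks like rounding to tablet strengths.

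**Conclusion.** Wrong as written, minor. For the case it states, the protocol's only numeric taper gives conflicting doses at most weights below 60 kg. A mid-band patient truly on 1 mg/kg who is dosed from the weight-band cell has a first cut of 50, 40, 36, 33 or 32% instead of 25%. These figures assume a patient exactly at the 1 mg/kg ceiling and a site that picks the cell by weight. The documents do not say how sites would use the table, so this is a possible use, not an instructed one.

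A reader might infer that efficacy results are at risk; the documents do not support that. Tapering starts at Week 2 at the earliest, after the Week 2 assessments, and needs an ACR50 response and a fever-free week. The primary endpoint and the Week 1 key secondary endpoints are therefore untouched. SAP 12.4.5 is descriptive, and the Week 12 at-least-50% count is the same on both readings for on-schedule tapers begun at Week 2, 4 or 8. What can move is the descriptive percentage decrease at earlier weeks and, for a Week 8 start, at Week 12. SAP 4.2 expects at least 12 patients instead of 81, so few will be exposed, although in so small a group one patient's taper can shift a mean.

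**What to change.** State the steps as a percentage of the patient's own baseline dose: 75%, 50%, 25%, about 12%, then off, each rounded to available strengths. This works at any weight and for any starting dose below the ceiling. If mg examples are kept, label their columns by actual starting dose instead of body weight, with no overlap.

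The cost is a one-page corrected appendix and a short note to sites for patients still to taper. The SAP needs no change.

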Appendix 5 Schedule of assessments

Assessments - page 1(2)	Screening visit (optional)	Visit 1	Tel f-up	Visit 2	Visit 3	Visit 4	Visit 5	Visit 6	Tel f-up	Study Drug Discontinuation visit
		Day 1	Day 4 _{Tel} (+/-2 days)	Week 1 (+2 days)	Week 2 (+2 days)	Week 4 (+/-2 days)	Week 8 (+/-2 days)	Week 12 (+/-2 days)	Week 16 _{Tel} (+5 days)	
				Day 8	Day 15	Day 29	Day 57	Day 85	Day 113	
Informed consent	X	X								
Eligibility criteria	X	X								
Randomization		X								
Medical history & Demographics		X								
Vital signs										
Blood pressure		X		X	X	X	X	X		X
Heart rate		X		X	X	X	X	X		X
Body weight		X		X	X	X	X	X		X
Height		X								
Physical examination		X		X	X	X	X	X ⁵		X ⁵
ECG		X								
Prior and/or concomitant medication		X		X	X	X	X	X	X	X
Blood Collection										
Laboratory assessments (incl. CRP)		X		X ³	X ⁷	X	X	X		X ⁶
Immunogenicity assessments		X		X	X	X	X	X		X
IL-1Ra/anakinra serum concentration		X		X	X	X	X	X		X
Inflammatory biomarkers (IL-6, IL-18, calprotectin, neopterin)		X		X	X			X		X
Exploratory pharmacogenetics markers					X ⁴					

¹ Assessment performed by blinded, trained and independent joint assessor.

² A diary will be used for daily recordings of fever episodes, patient's assessment of rash and time point of IMP administrations.

³ For patients with a body weight <15 kg hematology and coagulation samples should not be repeated at visit Week 1, if not clinically indicated, in order to preserve blood volume.

⁴ Any time after randomization.

⁵ For evaluating inactive disease, the following signs will specifically be recorded: rash, serositis, splenomegaly, hepatomegaly and generalized lymphadenopathy.

⁶ All laboratory assessments should be performed also for patients <15 kg body weight.

⁷ If the Week 2 visit is performed after the Study Drug Discontinuation visit, central lab should also be collected at the Week 2 visit, if not exceeding the maximum allowed blood volume collection according to limitations in relation to the body-weight of the patient.

Assessments - page 2(2)	Screening visit (optional)	Visit 1	Tel f-up	Visit 2	Visit 3	Visit 4	Visit 5	Visit 6	Tel f-up	Study Drug Discontinuation visit
		Day 1	Day 4 _{Tel} (± 2 days)	Week 1 (+2 days)	Week 2 (+2 days)	Week 4 (+/-2 days)	Week 8 (+/-2 days)	Week 12 (+/-2 days)	Week 16 _{Tel} (+ 5 days)	
				Day 8	Day 15	Day 29	Day 57	Day 85	Day 113	
Efficacy Assessments										
Physician global assessment of disease activity (VAS)		X		X	X	X	X	X		X
Patient/parent global assessment of overall well-being (VAS)		X		X	X	X	X	X		X
Number of joints with active arthritis ¹		X		X	X	X	X	X		X
Number of joints with limitation of motion ¹		X		X	X	X	X	X		X
Physical function (CHAQ or SHAQ)		X		X	X	X	X	X		X
Global assessment of the patient disease related pain (VAS)		X		X	X	X	X	X		X
Morning stiffness								X		X
Completion of diary ²					X					
Recording of absenteeism from school or work				X	X	X	X	X		X
Adverse events		X	X	X	X	X	X	X	X	X
IMP administration (at site)		X								
IMP dispensing		X		X	X	X	X			

¹ Assessment performed by blinded, trained and independent joint assessor.

² A diary will be used for daily recordings of fever episodes, patient's assessment of rash and time point of IMP administrations.

³ For patients with a body weight <15 kg hematology and coagulation samples should not be repeated at visit Week 1, if not clinically indicated, in order to preserve blood volume.

⁴ Any time after randomization.

⁵ For evaluating inactive disease, the following signs will specifically be recorded: rash, serositis, splenomegaly, hepatomegaly and generalized lymphadenopathy.

⁶ All laboratory assessments should be performed also for patients <15 kg body weight.

⁷ If the Week 2 visit is performed after the Study Drug Discontinuation visit, central lab should also be collected at the Week 2 visit, if not exceeding the maximum allowed blood volume collection according to limitations in relation to the body-weight of the patient.

Appendix 6 Schedule of repeated PK assessments Week 12

The assessments described below are **additional** assessments for patient enrolled to the repeated-dose PK sampling. All patients that do the repeated-dose PK assessments are also assessed according to schedule of assessments in Appendix 5.

	Visit 1	Tel f-up	Visit 2	Visit 3	Visit 4	Visit 5	Visit 6	Tel f-up
	Day 1	Day 4 ^{Tel} (+/-2 days)	Week 1 (+2 days)	Week 2 (+2 days)	Week 4 (+/- 2 days)	Week 8 (+/- 2 days)	Week 12 (+/- 2 days)	Week 16 ^{Tel} (+/- 2 days)
			Day 8	Day 15	Day 29	Day 57	Day 85	Day 113
Blood collection - repeated-dose pharmacokinetics								
Pre-dose							X	
2h after dose							X	
4h after dose							X ¹	
6h after dose							X ¹	
8h after dose							X	
IMP administration (at site)							a, X	

¹If exceeding maximum allowed blood volume for any patient, the samples at 4 and 6 hours may be replaced by a sample at 5 hours
a No administration of IMP at home before the visit

Appendix 7 Physician global assessment of disease activity

The physician will rate the patient's current condition on a 0-100 mm VAS, ranging from no disease activity (0 mm) to very severe disease activity (100 mm).

The below question will be answered by the investigator.

“Considering all the ways that Still's disease affects your patient, how would you rate his or her condition today?”

Please place a single mark on the line below.

Very well 0 |—————| 100 Very poor

Note: The VAS above is not presented in accurate length

The result of the investigator's assessment of the patient's disease activity should be withheld from the patient to minimize influencing his/her own assessment.

Appendix 8 Patient/parent global assessment of overall well-being

The patient or parent global assessment of overall well-being will be assessed on a 0-100 mm VAS, from very well (0 mm) to very poor (100 mm).

For patients <18 years of age at randomization, this question will be collected as a part of the CHAQ (see Appendix 9).

For patients \geq 18 years of age at randomization, this question will be collected as a part of the SHAQ (see Appendix 9).

Appendix 9 Physical function (CHAQ/SHAQ)

Parent proxy reporting CHAQ for children <18 years old:

 SUBJECT ID: _____ DATE COMPLETED: _____ 1-2

CHILDHOOD HEALTH ASSESSMENT QUESTIONNAIRE

In this section we are interested in learning how your child's illness affects his/her ability to function in daily life. Please feel free to add any comments on the back of this page. In the following questions, please check the one response which best describes your child's usual activities (averaged over an entire day) **OVER THE PAST WEEK, ONLY NOTE THOSE DIFFICULTIES OR LIMITATIONS WHICH ARE DUE TO ILLNESS**. If most children at your child's age are not expected to do a certain activity, please mark it as "Not Applicable". For example, if your child has difficulty in doing a certain activity or is unable to do it because he/she is too young but not because he/she is RESTRICTED BY ILLNESS, please mark it as "NOT Applicable".

		Without ANY Difficulty	With SOME Difficulty	With MUCH Difficulty	UNABLE To do	Not Applicable
3	DRESSING & GROOMING					
4	Is your child able to:					
6	Dress, including tying shoelaces and doing buttons?					
7	Shampoo his/her hair?					
8	Remove socks?					
9	Cut fingernails?					
10	ARISING					
11	Is your child able to:					
12	Stand up from a low chair or floor?					
13	Get in and out of bed or stand up in a crib?					
14	EATING					
15	Is your child able to:					
16	Cut his/her own meat?					
17	Lift up a cup or glass to mouth?					
18	Open a new cereal box?					
19	WALKING					
20	Is your child able to:					
21	Walk outdoors on flat ground?					
22	Climb up five steps?					
23	Please check any AIDS or DEVICES that your child usually uses for any of the above activities:					
24	Cane		- Devices used for dressing (button hook, zipper pull, long-handled shoe horn, etc.)			
25	Walker		- Built up pencil or special utensils			
26	Crutches		- Special or built up chair			
27	Wheelchair		- Other (Specify: _____)			
28	Please check any categories for which your child usually needs help from another person BECAUSE OF ILLNESS:					
29	Dressing and Grooming		- Eating			
30	Arising		- Walking			

I confirm that the information on this module is accurate.	Patient's initials:	Date:
Investigator's name:	Staff's initials:	Date:

© Singh G: Arthritis Rheum 1994; 37:1764-9. For information and permission to use, please contact [contact]

		Without ANY Difficulty	With SOME Difficulty	With MUCH Difficulty	UNABLE To do	Not Applicable
31						
32	HYGIENE					
33	Is your child able to:					
34	- Wash and dry entire body?					
35	- Take a tub bath (get in and out of tub)?					
36	- Get on and off the toilet or potty chair?					
37	- Brush teeth?					
38	- Comb/brush hair?					
39	REACH					
40	Is your child able to:					
41	- Reach and get down a heavy object such as a large game or books from just above his/her head?					
42	- Bend down to pick up clothing or a piece of paper from the floor?					
43	- Pull on a sweater over his/her head?					
44	- Turn neck to look back over shoulder?					
45	GRIP					
46	Is your child able to:					
47	- Write or scribble with pen or pencil?					
48	- Open car doors?					
49	- Open jars which have been previously opened?					
50	- Turn faucets on and off?					
51	- Push open a door when he/she has to turn a door knob?					
52	ACTIVITIES					
53	Is your child able to:					
54	- Run errands and shop?					
55	- Get in and out of a car or toy car or school bus?					
56	- Ride bike or tricycle?					
57	- Do household chores (e.g. wash dishes, take out trash, vacuuming, yardwork, make bed, clean room)?					
58	- Run and play?					
59	* Please check any AIDS or DEVICES that your child usually uses for any of the above activities:					
60	- Raised toilet seat					
61	- Bathtub seat					
62	- Jar opener (for jars previously opened)					
63	* Please check any categories for which your child usually needs help from another person BECAUSE OF ILLNESS:					
64	- Hygiene					
65	- Reach					
66	PAIN: We are also interested in learning whether or not your child has been affected by pain because of his or her illness. How much pain do you think your child has had because of his/her illness IN THE PAST WEEK? Place a mark on the line below, to indicate the severity of the pain					
67	No pain 0 ----- 100 Very severe pain					
68	GLOBAL EVALUATION: Considering all the ways that arthritis affects your child, rate how he/she is doing by placing a single mark on the line below.					
69	Very well 0 ----- 100 Very poor					

I confirm that the information on this module is accurate.	Patient's initials:	Date:
Investigator's name:	Staff's initials:	Date:

© Singh G: Arthritis Rheum 1994; 37:1764-9. For information and permission to use, please contact [contact]

SHAQ for patients ≥18 years old:

SUBJECT ID: _____

HAQ 1-6

HEALTH ASSESSMENT QUESTIONNAIRE				
Was assessment completed? No  (If no, give reason in comments) Yes 				
Date completed: _____ <small style="text-align: center;">day/month/year</small>				
In this section we are interested in learning how your illness affects your ability to function in daily life.				
Please check the response which best describes your usual abilities OVER THE PAST WEEK:				
DRESSING & GROOMING	Without ANY Difficulty	With SOME Difficulty	With MUCH Difficulty	UNABLE To Do
Are you able to:				
- Dress yourself, including tying shoelaces and doing buttons?				
- Shampoo your hair?				
ARISING				
Are you able to:				
- Stand up from a straight chair?				
- Get in and out of bed?				
EATING				
Are you able to:				
- Cut your meat?				
- Lift a full cup or glass to your mouth?				
- Open a new milk carton?				
Comments:				
Copyright© 1980 [name]. – Stanford, CA, U.S.A. - All Rights Reserved				
I confirm that the information on this module is accurate.	Patient's initials:	Date:		
Investigator's name:	Staff's initials:	Date:		

English for USA - V11

SUBJECT ID: _____

HAQ2-6

HEALTH ASSESSMENT QUESTIONNAIRE				

Please check the response which best describes your usual abilities OVER THE PAST WEEK:
				
WALKING	Without ANY Difficulty	With SOME Difficulty	With MUCH Difficulty	UNABLE To Do
Are you able to:				
- Walk outdoors on flat ground?				
- Climb up five steps?				

Please check any AIDS or DEVICES that you usually use for any of the activities on pages 1 and 2:
				
 Cane	 Crutches	 Built up or special utensils		
 Walker	 Wheelchair	 Special or built up chair		
 Devices used for dressing				
 Other (specify) _____				

Please check any categories for which you usually need HELP FROM ANOTHER PERSON:
				
 Dressing and Grooming	 Arising	 Eating	 Walking	
<small>Copyright© 1980 [name]. – Stanford, CA, U.S.A. - All Rights Reserved</small>				
I confirm that the information on this module is accurate.	Patient's initials:	Date:		
Investigator's name:	Staff's initials:	Date:		

English for USA - V11

SUBJECT ID: _____

HAQ₃₋₆

HEALTH ASSESSMENT QUESTIONNAIRE				

Please check the response which best describes your usual abilities OVER THE PAST WEEK:
				
	Without ANY Difficulty	With SOME Difficulty	With MUCH Difficulty	UNABLE To Do
HYGIENE				
Are you able to:				
- Wash and dry your body?				
- Take a tub bath?				
- Get on and off the toilet?				
REACH				
Are you able to:				
- Reach and get down a 5 pound object from just above your head?				
- Bend down to pick up clothing from the floor?				
GRIP				
Are you able to:				
- Open car doors?				
- Open jars which have been previously opened?				
- Turn faucets on and off?				
Copyright© 1990 [name]. – Stanford, CA, U.S.A. - All Rights Reserved				
I confirm that the information on this module is accurate.	Patient's initials:	Date:		
Investigator's name:	Staff's initials:	Date:		

English for USA - V11

SUBJECT ID: _____

HAQ4-6

HEALTH ASSESSMENT QUESTIONNAIRE				

Please check the response which best describes your usual abilities OVER THE PAST WEEK:
				
ACTIVITIES	Without ANY Difficulty	With SOME Difficulty	With MUCH Difficulty	UNABLE To Do
Are you able to:				
- Run errands and shop?				
- Get in and out of a car?				
- Do chores such as vacuuming or yardwork?				

Please check any AIDS or DEVICES that you usually use for any of the activities (hygiene, reach, gripping & opening things, errands & chores):
				
 Raised toilet seat			 Bathtub bar	
 Bathtub seat			 Long-handled appliances for reach	
 Jar opener (for jars previously opened)			 Long-handled appliances in bathroom	
 Other (specify) _____				

Please check any categories for which you usually need HELP FROM ANOTHER PERSON:
				
 Hygiene	 Reach	 Gripping and opening things	 Errands and chores	
<small>Copyright© 1980 [name]. – Stanford, CA, U.S.A. - All Rights Reserved</small>				
I confirm that the information on this module is accurate.	Patient's initials:	Date:		
Investigator's name:	Staff's initials:	Date:		

English for USA - V11

SUBJECT ID: _____

HAQ 5-6

HEALTH ASSESSMENT QUESTIONNAIRE

How much pain have you had because of your illness IN THE PAST WEEK?

Place a vertical (|) mark through the line to indicate the severity of the pain.

Copyright© 1980 [name]. – Stanford, CA, U.S.A. - All Rights Reserved

I confirm that the information on this module is accurate.	Patient's initials:	Date:
Investigator's name:	Staff's initials:	Date:

English for USA - V11

[figure not shown]

SUBJECT ID: _____

HAQ₆₋₆

HEALTH ASSESSMENT QUESTIONNAIRE

Considering all the ways your illness affects you, place a vertical (|) mark through the line to indicate how well you are doing.

Copyright© 1980 [name]. – Stanford, CA, U.S.A. - All Rights Reserved

I confirm that the information on this module is accurate.	Patient's initials:	Date:
Investigator's name:	Staff's initials:	Date:

English for USA - V11

